11.5 Analysis Plan

Data analysis will be performed using SAS or S-plus, as appropriate. All patients will be included in the intent-to-treat analysis for efficacy. Demographic and disease characteristics of the patients at registration will be summarized using descriptive statistics such as mean, standard deviation (SD), median and range. The RR for both arms will be estimated by Bayesian posterior estimates, along with the 95% credible intervals. The posterior probability that one treatment is better than the other will be computed, and the 95% credible interval of the posterior probability will also be estimated. The time-to-event variables will be estimated by Kaplan-Meier method. The survival difference between the two treatment schedules will be compared by Log-rank test. The OS is defined as the time period from the start of treatment till death or last follow-up whichever comes first. Duration of response (DoR) is for the patients who achieve CR or CRi, and it is defined as the time between the date of response confirmed (CR or CRi) and the date of progression or death (whichever occurs first). DoR will be censored on the date of last follow-up.

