1.0 Objectives

- **1.1 Primary**: Compare the response rates of two schedules of decitabine in patients with AML 60 and older than 60 and/or unfit for standard cytotoxic chemotherapy.
- **1.2 Secondary**: Compare response durations, survivals and side effects of the two schedules.
- **1.3 Tertiary**: To examine the correlation of a number of biological and pharmacodynamics correlates with response to therapy including global and gene-specific methylation, specific somatic gene mutations, micro-RNA, and immune effector function

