11.0 Statistical Considerations

11.1 General description

This is a Phase II open-label, efficacy and toxicity study of two treatment arms (arm A: Decitabine 20mg/m^2 IV daily for 5 days versus arm B: Decitabine 20mg/m^2 IV daily for 10 days) in subjects with AML ≥ 60 or unfit for standard cytotoxic chemotherapy. Patients will be enrolled to evaluate the 2 dose schedules. For both arms, one course will consist of 4 weeks. An adaptive randomization design will be employed to compare the efficacy between the two arms. The primary efficacy outcome is the complete response which is defined as the complete remission (CR) or complete remission with incomplete recovery (CRi) assessed after three cycles. At the end of the trial, we will estimate the probability that one arm is superior to the other. We will also evaluate toxicity on each arm. A maximum of 100 patients will be accrued, at an expected accrual rate of 5 patients per month.

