11.3 Study Design

A maximum of 100 patients will be adaptively randomized into two treatment groups:

Arm A: Decitabine 20mg/m2 IV daily for 5 days

Arm B: Decitabine 20mg/m2 IV daily for 10 days

Patients will be assigned to receive different schedules of Decitabine, using an adaptive procedure that bases assignment probabilities on observed results in preceding patients. At first, 20 patients will be assigned to each arm with equal probability. As efficacy data accrues, patient assignment to the two arms will become unbalanced in favor of the one that has the higher complete response rate (RR). The RR for both arms will be estimated with a 95% CI (similar to Bayesian highest posterior density interval).⁴⁹

Based on previous studies, we expect a RR of about 30% in both arms. Therefore, we assume RR has a prior Beta distribution (0.6, 1.4) with mean 0.3. Let RRa and RRb denote the response rates for arm A and arm B, respectively. Beginning with the 21st patient in each arm and for each subsequent patient, we will compare RRa with RRb, incorporating data from all patients with evaluable response. In order to avoid favoring one arm earlier in a large trial, instead of assigning patients with posterior probability (Pa=Pr(RRa>RRb|data) and Pb=1-Pa), we use the following formula to assign patients:

2012-1017 May 24, 2017 Page **23** of **29**

Aa= $\frac{\sqrt{Pa}}{\sqrt{Pa} + \sqrt{Pb}}$, Ab=1-Aa, where Aa is the probability of assigning patients to arm A, Ab is the

probability of assigning patients to arm B, Pa is the posterior probability that arm A is superior to arm B and Pb is the posterior probability that arm B is superior to arm A.

If at any point during the trial Pr(RRa>RRb|data)>0.95(or <0.05) the schedule A(or B) will be selected as superior. If accruing information gives strong evidence that a RR of 30% or greater is unlikely to be true for any one of the treatment arms (Pr(RRa or RRb>0.3|data)<0.05), assignment to that arm will be stopped. If the maximum of 100 patients is enrolled and evaluated and Pr(RRa>RRb|data)>0.9 (or <0.1), we will declare that arm A(or B) has a higher RR rate than arm B (or A). Otherwise, the trial will be inconclusive. We used simulation (5,000 simulations per scenario) to evaluate the performance of the adaptive randomization procedure under several different scenarios (Table 2). Adaptive Randomization version 4.1 has been used for the simulation. Adaptive Randomization version 4.1 has been used for the simulation.

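### Section 11.5 plans a 95% credible interval for the posterior probability of superiority, which is a single number and has none, while no interval is planned for the difference between arms

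*Combined protocol and SAP*

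**What the plan says.** The primary objective in section 1.0 is comparative: "Compare the response rates of two schedules of decitabine". Section 11.1 states how the comparison will be summarised: "At the end of the trial, we will estimate the probability that one arm is superior to the other".

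Section 11.3 sets up the model. For the response rates RRa and RRb, "we assume RR has a prior Beta distribution (0.6, 1.4) with mean 0.3", with no further prior on the parameters of that Beta distribution. It then defines the comparative quantity: "Pa is the posterior probability that arm A is superior to arm B". This Pa enters the square-root allocation formula. It is also compared with 0.95 and 0.05 during the trial and with 0.9 and 0.1 at the end ("If the maximum of 100 patients is enrolled and evaluated").

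Section 11.5 lists the efficacy deliverables. Each arm's response rate gets a posterior estimate and a 95% credible interval; section 11.3 also plans a 95% interval per arm. Then "The posterior probability that one treatment is better than the other will be computed", and the same sentence adds that "the 95% credible interval of the posterior probability will also be estimated". Neither section plans an interval for a difference, ratio or odds ratio of response rates.

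**The concern.** A credible interval describes the posterior distribution of an unknown quantity. The response rates are unknown and have posterior distributions. Pr(RRa>RRb|data) is obtained by integrating over both of those distributions, so nothing uncertain is left in it once the data are fixed. Asking for its 95% credible interval asks for something the stated model does not contain.

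Two things follow. The analyst must guess what was meant, and one possible guess, an interval over simulation draws, would look like a precise inferential statement while depending only on the number of draws. In addition, the interval that would serve the primary objective, on the size of the difference between schedules, is not pre-specified. The probability of superiority already gives the chance that the selected arm is the worse one, and a point difference can be derived from the per-arm results. The plan does not provide for a range showing how large the difference could plausibly be.

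**Working it through.** The documents give no figure for this interval, so there is nothing to reproduce. The check uses the plan's own model.

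**Inputs from section 11.3.** Prior Beta(0.6, 1.4) for each arm; maximum of 100 patients; final threshold 0.9; early threshold 0.95. All response counts below are assumptions for illustration.

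**Model.** With s responders among n patients, an arm's posterior is Beta(0.6 + s, 1.4 + n − s), independently by arm.

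**Step 1: the probability is one number.** Pr(RRb>RRa|data) = ∫ f_B(t) F_A(t) dt over 0 to 1, where f_B is the posterior density for arm B and F_A the posterior distribution function for arm A. Both are fully determined by the counts and the fixed prior.

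- 15/50 on A, 22/50 on B: posteriors Beta(15.6, 36.4) and Beta(22.6, 29.4); Pr(RRb>RRa|data) = 0.9253.
- 12/40 on A, 26/60 on B: posteriors Beta(12.6, 29.4) and Beta(26.6, 35.4); Pr(RRb>RRa|data) = 0.9135.

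Both cases total 100 patients and fall between 0.9 and 0.95, so the final rule applies and arm B is declared to have the higher rate.

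**Step 2: literal attempts at the planned interval.**

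- *Simulation draws.* The Monte Carlo 95% half-width is 1.96 × √(p(1 − p)/N). With p = 0.9253 and N = 1,000 it is 1.96 × √(0.9253 × 0.0747/1,000) = 0.0163, giving 0.909 to 0.942. With N = 1,000,000 it is 0.0005, giving 0.9248 to 0.9258. The data are the same; the width shrinks towards zero as N grows.
- *The event itself.* RRb>RRa is either true or false. The central 95% range of that indicator for 15/50 v 22/50 is 0 to 1, which says nothing.

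**Step 3: the interval that does exist.** The difference RRb − RRa has a posterior distribution under the same two Beta posteriors. Numerical integration gives:

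| Assumed data (A v B) | Pr(RRb>RRa) | Posterior median of RRb − RRa | Equal-tailed 95% credible interval |
|---|---|---|---|
| 15/50 v 22/50 | 0.9253 | 13.5 points | −4.9 to +31.4 points |
| 12/40 v 26/60 | 0.9135 | 13.0 points | −5.8 to +30.8 points |

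**Step 4: an early selection.** At the end of the equal-allocation stage, assumed counts of 6/20 v 13/20 give Pr(RRb>RRa) = 0.986, above the 0.95 rule. The difference has posterior mean 31.8 points and 95% credible interval 3.4 to 57.7, a width of 57.7 − 3.4 = 54.3 points. Here too the probability alone does not convey how poorly the size of the difference is known.

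**The case against.** The strongest reply is that the plan chose its comparative measure deliberately. Section 11.1 names the probability of superiority, section 11.3 gives it cut-offs, and section 11.5 adds an estimate and interval for each arm. For a phase II trial that ends by saying which arm has the higher rate, that is coherent, and the lack of an interval for the difference contradicts nothing. This is fair as far as it goes: the missing contrast interval is a gap in reporting, not an inconsistency. The interval for the difference still cannot be read off the two separate per-arm intervals, and the plan names no contrast.

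A second reply is that the illustrations prove little. Any probability between 0.9 and 0.975 gives an equal-tailed 95% interval that includes zero, so that feature reflects the 0.9 threshold and not the faulty clause. This stands, and the examples are not offered as evidence against the threshold. Nor are they typical selections. In Table 2, Pr(Select) minus Pr(Select Early) for arm B is 0.66 − 0.52 = 0.14 at true rates 0.1 v 0.3, and 0.01, 0.03 and 0.05 at 0.3 v 0.65, 0.3 v 0.3 and 0.5 v 0.6, so most selections in these scenarios come early. The examples show only what the missing interval would tell the reader.

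Third, nothing says the final probability will be computed by simulation; the simulations described in section 11.3 concern operating characteristics. That is correct. The Monte Carlo figures show why one literal reading fails, not what the sponsor is expected to do.

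Finally, the clause may simply be a slip for an interval on the difference. That is plausible, and if so the correction below states what was meant. The text does not say it, and as written it cannot be carried out.

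**Conclusion.** The concern holds. The credible interval requested in section 11.5 is undefined under the model in section 11.3, and no interval for a between-arm response contrast is pre-specified although the primary objective is to compare response rates. The first part is a matter of definition: it rests only on the priors being fixed, as section 11.3 states. The sizes in the examples rest on assumed counts and on independent Beta posteriors.

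Severity is minor. Allocation, early selection, futility stopping and the final declaration all use the probability as a single value or the per-arm posteriors, and none uses this clause. What is affected is the reporting of the primary comparison.

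**What to change.** In section 11.5, replace the clause about an interval on the posterior probability with:

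> Pr(RRb>RRa|data) will be reported as a single number, together with the posterior median and equal-tailed 95% credible interval of the difference RRb − RRa under the priors in section 11.3.

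Section 11.3 likens its per-arm interval to a highest posterior density interval. If the sponsor prefers that type for the difference, the sentence should say so; in the two 100-patient examples the choice moves each limit by only about 0.2 to 0.3 of a percentage point. The type should be named either way.

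The cost is one sentence. The same two Beta posteriors give the result, with no new data, no new simulation of the design and no change to any decision rule.

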Other factors that are clearly important predictors of outcome include patient-related factors such as organ function, and presence of uncontrolled infection, and leukemia-related factors such as biological determinants of resistance to chemotherapy. Cytogenetics has been clearly established as one of the most important predictors of outcome in AML.¹³⁻¹⁵ ¹⁶ Although the overall outcome of older patients with AML is inferior to younger adults, survival is generally improved for patients with favorable and intermediate cytogenetic aberrations compared to those with adverse karyotype. Recent data confirm the importance of pretreatment karyotype on the outcome of older patients.¹⁷⁻²⁰ In a report examining the prognostic factors in older patients treated on the MRC AML11 and AML14 trials, the survival was very much dependent on the cytogenetic risk. In another study by the German-Austrian AML study group high risk cytogenetics and age above 70 years were independent prognostic factors affecting overall survival.¹⁹ Stratification using these parameters identified a large subgroup (55%) of patients with very poor outcome despite intensive chemotherapy. Whether pretreatment cytogenetics should be factored in the choice of therapy in older AML patients remains a subject of debate. As typically the result of this analysis may not be available for up to a week, it can be argued that cytogenetics should not influence the initial decision making process in selecting therapy. However, a recent study by Sekeres and colleagues demonstrated that accounting for other covariates available at the time of diagnosis, in patients older than 60 years and with white blood cell (WBC) less than 50 x 10⁹/L, time from diagnosis to initiation of therapy did not affect CR rate or overall survival suggesting that this population may not be harmed from a delay to obtain the results of additional testing.²¹ Others have also recommended waiting until the cytogenetic results are available.²² Obviously, this is highly dependent on the availability of treatment strategies that are clearly superior to standard in particular cytogenetic subgroups or the recognition that patients with specific characteristics such as those described by Malfuson and colleagues are unlikely to benefit from standard induction regimens.²²

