In another phase II clinical trial with decitabine in older patients (>or=60 years) with previously untreated AML who were not candidates for or who refused intensive chemotherapy, subjects received low-dose decitabine at 20 mg/m² i.v. over 1 h on days 1 to 10. Fifty-three patients were enrolled with a median age of 74 years (range, 60-85).⁴⁷ Nineteen (36%) had antecedent hematologic disorder or therapy-related AML; 16 had complex karyotypes (>or=3 abnormalities). The complete remission rate was 47% (n = 25), achieved after a median of three cycles of therapy. Nine additional subjects had no morphologic evidence of disease with incomplete count recovery, for an overall response rate of 64% (n = 34). Complete remission was achieved in 52% of subjects presenting with normal karyotype and in 50% of those with complex karyotypes. Median overall and disease-free survival durations were 55 and 46 weeks, respectively. Death within 30 days of initiation of treatment occurred in one subject (2%), death within 8 weeks in 15% of subjects. They also examined the relationship of clinical response and pretreatment level of miR-29b, previously shown to target DNA methyltransferases. Higher levels of miR-29b were associated with clinical response (P = 0.02). They concluded that this schedule of decitabine was highly active and well tolerated in this poor-risk cohort of older AML patients and suggested that levels of miR-29b should be validated as a predictive factor for stratification of older AML patients to decitabine treatment.⁴⁷

Most recently a multicenter, randomized, open-label, phase III trial compared the efficacy and safety of decitabine with treatment choice (TC) in older patients with newly diagnosed acute myeloid leukemia (AML) and poor- or intermediate-risk cytogenetics.⁴⁸

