6.1 Gene-mutations effecting methylation machinery

Mutations of several genes believed to be important in the methylation apparatus of the cell have been recently described in patients with acute myeloid leukemia (AML) but their presence has not been correlated with a worse or better outcome using hypomethylating agents. We have previously evaluated the association of mutations in IDH1. IDH2. DNMT3A. and EZH2 with the outcome [complete response (CR) rate, event free survival (EFS) and overall survival (OS)] among patients older than 60 with AML (≥ 20% blasts) treated with hypomethylating agents as their first line of treatment. TET2 mutations were not evaluated due to lack of available material. Among the 68 patients (median age 72 years; range, 60 - 83) with available data, 11 patients (16%) had IDH1 or IDH2 mutations (mutually exclusive) and 10 patients (15%) had DNMT3A mutations with 5 patients (7%) having both IDH and DNMT3A mutations. Cytogenetics was diploid in 19 (28%), abnormal chromosome 5/7 and/or complex in 27 (40%), trisomy 8 in 5 (7%), miscellaneous in 14 (21%), and insufficient in 3 (4%). Presence of *IDH* mutations was associated with a diploid karyotype and the presence of *NPM1* mutations (p=.03 and p=.02, respectively) but not with FLT3-ITD or RAS mutations (present in 7 and 4 patients, respectively). DNMT3A mutations were not associated with any specific karyotype or with the presence of NPM1, FLT3-ITD, or RAS mutations. None of the 68 patients had EZH2 mutations. All patients were treated with hypomethylating agents [decitabine in 39 (57%) and 5-azacytidine in 29 (43%)] with 42 patients (62%) receiving concomitant histone deacetylase inhibitor therapy (SAHA or valproic acid). Overall, 17 patients (25%) achieved CR; the presence of IDH or DNMT3A mutations or both was not associated with achievement of CR. With a median duration of follow-up of 60 months, the median EFS is 3.3 months (range, 0.25 - 3.75 months) and the median overall survival is 6 months (range, 0.25 - 90.5 months). Presence of IDH mutations was not associated with an impact on EFS (p=.29) or OS (p=.14). Similarly, DNMT3A mutations were not associated with an effect on EFS (p=.21) or OS (p=.58). The presence of both IDH and DNMT3A mutations was also not associated with a better or worse response, EFS, or OS as compared with patients with neither mutation. We

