7.0 Pre-study evaluations (to be performed within 14 days unless otherwise noted)

- 7.1 History and physical exam.
- 7.2 CBC, platelet count, differential; creatinine, bilirubin, SGPT (within 7 days).
- 7.3 Bone marrow aspirate (within 14 days) and cytogenetics
- **7.4** Molecular studies in bone marrow specimens for FLT3-ITD, FLT3-TKD, NPM1, IDH1, IDH2, DNMT3A, TET2, EZH2, RAS, JAK2 (if appropriate, e.g. in patients

with history of MPN), and the Leukemia mutation panel (whichever is available at the time of enrollment)

- 7.5 Whole genome sequencing (performed at [name] laboratory)
- **7.6** Blood sample (20-50 cc) and marrow aspirate sample (2 cc) for methylation studies, to be sent to [name] laboratory. Not all samples may be collected at all times points and omissions will not be considered deviations. Samples obtained prior to consenting may be used.
- **7.7** Blood sample (25-35cc) will be collected for assessment of immune function and effector cells to be sent to [name] lab. Not all samples may be collected at all times points and omissions will not be considered deviations. Samples obtained prior to consenting may be used.
- **7.8** Pregnancy (urine or blood) test only for women of childbearing potential within 7 days.

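### Optional improvement: the only survival comparison is a log-rank test with no strata named, although cytogenetic risk is collected at baseline and described as strongly prognostic

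*Combined protocol and SAP*

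**What the plan says.** Survival is a secondary objective: Section 1.2 sets out to "Compare response durations, survivals and side effects of the two schedules". Section 11.5 plans Kaplan-Meier estimates, and then "The survival difference between the two treatment schedules will be compared by Log-rank test". It names no stratum, covariate or Cox model, and Sections 11.2 and 11.3 name no stratification factor for the randomisation. That the test is unstratified is inferred from this silence, but it is the natural reading. Section 11.5 also summarises disease characteristics at registration, so an imbalance could be seen, but nothing adjusts for one.

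On prognosis, Section 2.1.2 reports that in two earlier trials in older patients "the survival was very much dependent on the cytogenetic risk". Item 7.3 requires, before treatment, "Bone marrow aspirate (within 14 days) and cytogenetics".

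The documents' decitabine data point to little karyotype gradient in response. For the 10-day schedule, Section 2.3 reports: "Complete remission was achieved in 52% of subjects presenting with normal karyotype and in 50% of those with complex karyotypes". For the 5-day schedule it describes response as consistent across subgroups, poor-risk cytogenetics included.

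**The concern.** When a baseline factor predicts survival strongly, a log-rank test that ignores it loses efficiency and does not correct a chance imbalance in that factor. Both matter more in a small trial. This one enrols at most 100 patients and can stop much earlier: Table 2 expects 21.7 + 24 = 45.7 patients at response rates 0.3/0.65. If the arms then differ in karyotype, a reader who accepts Section 2.1.2 will ask whether that explains any survival difference. An adjusted analysis written in advance is a more credible answer than one chosen after the data are seen.

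**Working it through.** The documents state no death count, alpha, power or target HR for survival, so there is no survival figure to reproduce. The check asks what stratifying by karyotype would change.

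**Inputs from the documents**
- Section 11.3: 20 patients per arm, then square-root adaptive allocation; Beta(0.6, 1.4) priors; selection at posterior probability above 0.95 or below 0.05; an arm closes if Pr(RR > 0.3) < 0.05; maximum 100 patients.
- Section 11.1: 5 patients per month, response assessed after three 4-week cycles. The lag is 12 weeks, about 2.76 months, and 2.76 × 5 = 13.8, so about 14 patients.
- Section 2.3: median survival 7.7 months on the 5-day schedule.
- Section 6.1: adverse karyotype (chromosome 5/7 and/or complex) in 27/68 = 40% of an earlier series; insufficient karyotype in 3/68.

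**Assumptions**
- Treatment HR 0.6, two-sided 5%, exponential survival, 12 months of follow-up after the last patient.
- Karyotype HR 1, 1.5, 2 or 3.
- Response independent of karyotype and, in the main runs, of survival given arm.
- The toxicity stop in Section 11.4 is not modelled; it would reduce patients and deaths.

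**Step 1: the simulated design against Table 2.** Mean patients per arm (60,000 runs per setting) were 41.7/41.7, 36.9/42.1 and 22.4/25.2 at response rates 0.3/0.3, 0.5/0.6 and 0.3/0.65. Table 2 gives 40.2/40.3, 36.7/43 and 21.7/24. These are close.

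**Step 2: power, unstratified v stratified**

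| Response rates A/B | Karyotype HR 1 | HR 1.5 | HR 2 | HR 3 |
|---|---|---|---|---|
| 0.3/0.3 | 0.49 v 0.48 | 0.48 v 0.48 | 0.44 v 0.47 | 0.38 v 0.46 |
| 0.5/0.6 | 0.48 v 0.47 | 0.46 v 0.46 | 0.43 v 0.46 | 0.37 v 0.45 |
| 0.3/0.65 | 0.31 v 0.30 | 0.30 v 0.29 | 0.28 v 0.29 | 0.24 v 0.28 |

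Mean deaths were 60-62, 56-58 and 31-33. As a check at karyotype HR 1, Schoenfeld power is Φ(√(d/4) × |ln 0.6| − 1.960), with |ln 0.6| = 0.511:
- d = 61: Φ(1.995 − 1.960) = 0.51
- d = 57: Φ(1.928 − 1.960) = 0.49
- d = 32: Φ(1.445 − 1.960) = 0.30

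These agree with the first column to within about 2 points.

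**Step 3: sensitivity of the change in power**
- If responders have half the hazard: -1 to -2 points at karyotype HR 1, +1 to +2 at HR 2, +5 to +6 at HR 3.
- At karyotype HR 3: +6 to +9 points at treatment HR 0.5, and +2 to +5 at treatment HR 0.7.
- With insufficient karyotypes placed with all other: -1.1 to -1.3 points at karyotype HR 1, +3.8 to +7.6 at HR 3.

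**Step 4: chance imbalance.** With 40% adverse, the standard deviation of the between-arm gap is √(0.4 × 0.6 × (1/n₁ + 1/n₂)). At 20 per arm it is √(0.24 × 0.10) = 0.155, so a 20-point gap is 1.29 SD (about 20% of trials by the normal approximation). At 50 per arm it is √(0.24 × 0.04) = 0.098, so the gap is 2.04 SD (about 4%). Across the simulated mix of trial sizes, a gap of at least 20 points occurs in about 10% of trials in the first two scenarios and about 20% in the third, where at least half of trials end at 40 patients. In the trials with such a gap, the unstratified type I error is 0.06-0.07 at karyotype HR 1.5, 0.08-0.09 at HR 2 and 0.10-0.12 at HR 3, against about 0.05 stratified.

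**Step 5: type I error over all trials.** Both tests are at 0.051-0.056. Smaller adaptive simulations (4,000 runs per setting, standard error about 0.35 points), some with longer-lived responders or a drifting karyotype mix, gave 5.1-6.3% unstratified and 5.6-6.9% stratified. Stratifying does not improve overall error control.

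**Step 6: deaths needed.** For 80% power at HR 0.6: 4 × (1.960 + 0.842)² / (ln 0.6)² = 120.3, so 121 deaths. That exceeds the 100-patient maximum.

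**The case against.** The strongest reply is that nothing is broken. A log-rank test without strata matches a randomisation without strata, survival is secondary with no power claim, and the choice of strata is a preference. That stands as to severity: this is an optional improvement.

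The second reply is that the prognostic premise is not shown for this treatment. The statement in Section 2.1.2 rests on trials that Section 2.3 does not list among its decitabine studies, and the decitabine results by karyotype in Section 2.3 are nearly flat. This also stands, in part. Those results are for response, not survival, so they do not exclude a survival gradient, but no HR can be taken from the documents. That is why the range includes no effect, and why gains of 4 points or more appear only at the assumed karyotype HR of 3.

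Third, the raised type I error applies only to trials picked out for a large gap. Correct: it describes exposure to a chance imbalance, not the operating error rate.

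A reader might also infer that comparing the two tests would reveal whether imbalance drives a result. It would not. They disagree in about 5% of trials even at karyotype HR 1, where imbalance cannot matter, and in 9-18% at HR 2-3. For the same reason one test should be named as the main one, with an HR and interval that belong to it.

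**Conclusion.** The point holds as a cheap, optional improvement. Power changes by about -1 point (up to -2) if karyotype has no effect on survival, by about 0 at karyotype HR 1.5, by +1 to +3 at HR 2 and by +4 to +8 at HR 3. This rests on the assumed treatment HR of 0.6, two-sided 5%, 12 months of further follow-up and 40% adverse karyotype, with toxicity stopping left out. The other benefit is protection in the 10-20% of trials with a karyotype gap of at least 20 points.

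Two stronger readings are tempting and not supported. One is that the planned test is invalid: its overall type I error is about 5-6%, and no decision rule or stated figure uses survival. The other is that stratifying would make the survival comparison adequately powered: it would not, since 121 deaths are needed at HR 0.6 and at most 100 patients enter.

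**What to change.** Replace the log-rank sentence in Section 11.5 with:

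> The main OS comparison between schedules will be a log-rank test stratified by baseline cytogenetic risk (adverse = chromosome 5/7 abnormality and/or complex karyotype with at least 3 abnormalities, v all other; insufficient karyotype is placed with all other). The hazard ratio and 95% CI will come from a Cox model stratified by the same factor. The unstratified log-rank test, with its own unstratified hazard ratio and CI, will be reported as a sensitivity analysis.

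The grouping follows Section 6.1, and the definition of complex follows Section 2.3. Make the change before any OS comparison between arms, so that the main test is not chosen by its result.

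The cost is a few lines of text and no new data, plus about 1-2 points of OS power if karyotype does not predict survival on decitabine. The Bayesian response rule and Table 2 are unchanged.
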